Following are the rules for the monitoring of toxicities in the Phase II portion of the study. Toxicity will be defined as clinically significant non-hematologic drug related grade 3 or higher adverse events. The probability of toxicity is denoted by PE. We assume PE – beta (0.6, 1.4). Our stopping rule is given by the following probability statement: Probability (PE > 0.30 | data) > 0.975. That is, we will stop the study if, at any time during the study, we determine that there is more than 97.5% chance that the toxicity is more than 30%. This stopping rule will be applied in each cohort. The stopping boundaries for clinically significant toxicities observed during the first cycle, based on these assumptions and monitoring conditions found in table 10. We will apply these stopping boundaries starting from the fifth patient and in cohorts of 5. For example, accrual will cease if 4 patients experience clinically significant toxicities during the first cycle among the first 5 patients treated. The operating characteristics are summarized in table 11.

Table 10. Stopping boundaries for Phase II toxicities

The number of patients evaluated for toxicities	5	10	15	20	25	30	35	40	45	50	55	60
The number of patients with DLTs	4	5-6	7-8	9-10	11-12	13-14	15-16	17-18	19	20-21	22-23	24-25

Table 11. Operating characteristics

True Toxicity Rate	Early Stopping Probability	Sample Size		
		25 th percentile	Median	75 th percentile
0.10	0.008	60	60	60
0.20	0.010	60	60	60
0.30	0.082	60	60	60
0.40	0.474	30	60	60
0.50	0.906	15	25	40

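### Table 10's Phase II toxicity stopping counts contradict the stated posterior rule at 11 of 12 looks; read literally, they stop at 20–30% true toxicity more than three times as often as Table 11 says

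*Combined protocol and SAP*

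**What the plan says.** Section 10.3, Toxicity Monitoring, gives the Phase II toxicity probability PE a Beta(0.6, 1.4) prior. The rule is stated as a formula, "Our stopping rule is given by the following probability statement: Probability (PE > 0.30 | data) > 0.975", and again in words: stop if there is "more than 97.5% chance that the toxicity is more than 30" percent. On timing it says "We will apply these stopping boundaries starting from the fifth patient and in cohorts of 5".

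Table 10 is captioned as stopping boundaries and is said to rest on these assumptions. Its row for n = 5, 10, ..., 60 reads "The number of patients with DLTs 4 5-6 7-8 9-10 11-12 13-14 15-16 17-18 19 20-21 22-23 24-25". The worked example confirms that a printed count means stop: "accrual will cease if 4 patients experience clinically significant toxicities during the first cycle among the first 5 patients treated".

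Table 11 gives early-stopping probabilities of 0.008, 0.010, 0.082, 0.474 and 0.906 at true toxicity rates of 0.10, 0.20, 0.30, 0.40 and 0.50.

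**The concern.** The probability statement, the count table and the operating characteristics should be one rule in three forms. Table 10 is the form a study team would use at each look. If its counts are not those of the rule, two people working from the same section reach opposite decisions. With 5 or 6 toxicities in the first 10 patients, Table 10 halts accrual and the probability statement does not. Table 11 would then describe a different trial from the one Table 10 runs, and the chance of halting a regimen at or below the 30% limit would be understated.

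**Working it through.** **Inputs (all from section 10.3).** Prior Beta(0.6, 1.4); toxicity limit 0.30; posterior cut-off 0.975; looks every 5 patients from n = 5; maximum n = 60; Table 10 and Table 11 as printed.

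**Step 1: boundaries from the rule.** After x toxicities in n patients the posterior is Beta(0.6 + x, 1.4 + n − x). Stop at the smallest x whose posterior probability above 0.30 exceeds 0.975.

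- n = 5, x = 4: Beta(4.6, 2.4) gives 0.9751, so stop. This matches Table 10 and the worked example.
- n = 10, x = 5: Beta(5.6, 6.4) gives 0.880. x = 6 gives 0.963. Both continue; x = 7 is the first stop.

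| n | Table 10 | Posterior at lowest / highest printed count | Rule: first stopping count |
|---|---|---|---|
| 5 | 4 | 0.975 | 4 |
| 10 | 5-6 | 0.880 / 0.963 | 7 |
| 15 | 7-8 | 0.893 / 0.960 | 9 |
| 20 | 9-10 | 0.906 / 0.961 | 11 |
| 25 | 11-12 | 0.918 / 0.963 | 13 |
| 30 | 13-14 | 0.929 / 0.967 | 15 |
| 35 | 15-16 | 0.938 / 0.970 | 17 |
| 40 | 17-18 | 0.946 / 0.973 | 19 |
| 45 | 19 | 0.953 | 20 |
| 50 | 20-21 | 0.926 / 0.959 | 22 |
| 55 | 22-23 | 0.936 / 0.964 | 24 |
| 60 | 24-25 | 0.945 / 0.969 | 26 |

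From n = 10 on, no printed count passes 0.975. Each highest printed count is the rule's boundary minus 1. From n = 15 on, each lowest printed count is the rule's boundary at the previous look. That pattern suggests a construction slip in the row.

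**Step 2: early-stopping probabilities.** For a true rate p, the distribution of the running count is updated by adding a Binomial(5, p) cohort. At each look the mass at or above the boundary is moved to "stopped", and the rest carries on. The calculation is exact. Looks run from n = 5 to n = 55, because a stop at n = 60 is not early.

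| True rate | Table 11 | Rule | Table 10, lowest count as trigger | Table 10, highest count as trigger |
|---|---|---|---|---|
| 0.10 | 0.008 | 0.0005 | 0.002 | 0.001 |
| 0.20 | 0.010 | 0.008 | 0.046 | 0.015 |
| 0.30 | 0.082 | 0.083 | 0.277 | 0.151 |
| 0.40 | 0.474 | 0.471 | 0.740 | 0.607 |
| 0.50 | 0.906 | 0.906 | 0.976 | 0.950 |

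The rule reproduces Table 11 from 0.20 to 0.50, so Table 11 was computed from the rule and not from Table 10. The 0.10 row does not reproduce, but both values mean that the trial almost never stops. Including the n = 60 look changes little: at 0.30 the rule gives 0.086 and the lowest-count reading 0.280.

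Ratios to Table 11 with the lowest count as trigger: 0.277 / 0.082 = 3.4 at 0.30, and 0.046 / 0.010 = 4.6 at 0.20. With the highest count: 0.151 / 0.082 = 1.8 and 0.015 / 0.010 = 1.5. At 0.40 the median sample size is 20 on the lowest-count reading, against 60 in Table 11.

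**Step 3: effect on completing Phase II (illustrative).** Take true ORR 60% and true toxicity 30%, treated as independent. Under 40% response, 33 of 60 is the smallest count with an exact upper tail no greater than 0.025 (0.013; for 32 it is 0.02503). With Table 8's boundaries applied to n = 55, the chance of reaching 60 patients with at least 33 responses is 0.797. Multiplying by the chance of no toxicity stop gives 0.797 × (1 − 0.083) = 0.73 under the rule and 0.797 × (1 − 0.277) = 0.58 under Table 10's lowest counts.

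**The case against.** Four points can be made for the plan.

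*The cells may be the highest counts at which to continue.* If 1 is added to each upper end from n = 10 on, and 4 is kept at n = 5, all 12 looks match the rule. This probably explains how the row arose. It cannot be how the table is meant to be read, because the n = 5 cell would then mean the opposite of the other eleven, and the caption and worked example say that printed counts stop. Adding 1 at every look, including n = 5, gives 0.064 at 30% toxicity and contradicts the worked example.

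*The lower end may be only a formatting device.* Each lower end from n = 10 on is the previous cell's upper end plus 1, and in Table 8 the upper ends are the operative limits. But Table 8 stops for too few responses, so its upper end is the one next to the continue region. For toxicity that is the lower end. A list of stopping counts showing 5-6 at n = 10 stops at 5. The upper-end reading is possible, and it still gives 0.151 rather than 0.082. Taken as closed ranges, the cells give 0.276, and 7 toxicities in 10 would not stop at that look.

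*Phase I patients may count.* Section 10.2 includes 6 patients treated at the MTD in the 60, although section 3.2 adds 24 and 60 separately. If those six, with at most 1 DLT, were the first monitored, the lowest-count reading would stop with probability 0.087 at 30%, close to Table 11's 0.082. On that same assumption the rule itself stops with probability only 0.017, so the gap between table and rule remains.

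*The error is on the cautious side.* With either end of the range as the trigger, the table stops sooner than the rule. This stands: the cost is a false halt, not added exposure to toxicity. It is also true that 30% is the rule's own limit, so a regimen at that rate is borderline; one at 20% is not.

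**Conclusion.** The concern holds. Table 10 contradicts the stated rule at 11 of 12 looks, while the rule and Table 11 agree at true rates of 20% to 50%. At 30% true toxicity the printed counts stop early with probability 0.277 (lowest count as trigger) or 0.151 (highest), against 0.082 stated: 3.4 or 1.8 times. The figure of more than three times rests on the lowest-count reading and applies at true rates of 20% and 30%. It also assumes looks at exact multiples of 5 and no carry-over of Phase I patients. The boundary mismatch itself depends on none of these. The 0.73 against 0.58 comparison additionally assumes that toxicity and response are independent. The 0.10 row of Table 11 is a minor separate slip. Because the table governs whether accrual is halted, it must be corrected before use.

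**What to change.** Reconcile the probability statement, Table 10 and Table 11 so that all three express one rule.

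- If the stated rule stands, replace the Table 10 row with 4-5, 7-10, 9-15, 11-20, 13-25, 15-30, 17-35, 19-40, 20-45, 22-50, 24-55 and 26-60 at n = 5, 10, ..., 60. Running each range up to n removes the doubt about which end triggers the stop. Correct the 0.10 row of Table 11 to below 0.001; its other early-stopping probabilities can stay.
- If the stricter printed counts were intended, change the probability statement to one that yields them, state which end of each range is the trigger, and recompute Table 11.

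The first option changes one table row and one cell. The second changes one sentence and recomputes one table. Neither adds patients, visits or procedures.

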10.4 Statistical Analysis Plan

All patients who received at least 1 dose of the combination therapy will be included in the intent-to-treat analysis for efficacy and safety. Demographic/clinical characteristics and safety data of the patients will be summarized using descriptive statistics such as mean, standard deviation, median and range. Response rates will be presented with 95% confidence intervals. The association between response and patient and clinical characteristics will be examined by Wilcoxon's rank sum test or Fisher's exact test. Overall survival time will be estimated using the

Kaplan-Meier method. Patients who drop out of the study will be included in the time to event data as "censored data". The two-sided log-rank test will be used to assess the differences of time to events between groups.

11.0 DATA CONFIDENTIALITY PROCEDURES:

Samples are identified by patients' unique identification number, which allows patient identification and linkage to the clinical database. Because many of these studies require clinical correlation, the medical record number (MRN) is maintained in the Oracle database. Only designated users may view data associated with patient identifiers. Other users see only a unique patient identifier. Dates of birth are not available to general users, this information is only available to central personnel and it is used to calculate age, as part of data that may be important to correlate with research assay results. This database is password-protected.

12.0 REFERENCES:

2. Kantarjian HM. Therapy for elderly patients with acute myeloid leukemia: a problem in search of solutions. *Cancer* 2007;109:1007-1010.
4. Erba HP. Prognostic factors in elderly patients with AML and the implications for treatment. *Hematology / the Education Program of the American Society of Hematology American Society of Hematology Education Program* 2007:420-428.

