10.1 STATISTICS

10.2 Sample size

This will be a single arm, single center, open label study of the combination of vosaroxin with decitabine as an induction therapy in previously untreated patients with acute myeloid leukemia (AML) or high risk myelodysplastic syndrome (MDS) who are elderly (age \geq 60) and/or unable to tolerate standard therapy. A total of up to 84 patients will be enrolled in the study.

Phase I

A total of up to 24 patients will be accrued into the Phase I part.

Phase II

A total of up to 60 patients (including 6 patients treated at the MTD from the Phase I part) will be recruited for the Phase II part.

The primary efficacy endpoint is overall response rate (ORR). $ORR = CR + CR_p + CR_i$. Responses will be evaluated at the end of the first induction cycle and second induction cycle (if a second induction cycle is needed). With a null hypothesis of 40% historical response rate, a sample size of 60 patients would be required to demonstrate a response rate of 60% for the combination of vosaroxin and decitabine using a one-sample exact binomial test and with a two-sided alpha of 0.05 and a power of 82%.

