10.3 Statistical Design

Phase I

. In phase I portion of the study the MTD is defined as the highest daily oral dose evaluated at which $<33\%$ of patients experience a DLT. Six patients will be treated. If clinically significant drug related Grade 3-4 toxicity is observed during the first cycle in 0-1 patient out of 6 patients, this will define a safe schedule and the study will open broadly for the Phase II portion. If drug related Grade 3-4 toxicity is observed in 2 or more of 6 patients, this dose will exceed DLT, and a lower dose schedule will be investigated in an additional 6 patients. Please refer to Section 4.4. The dosing algorithm is presented in Table?.

Table 7. Dosing algorithm

Dose Level	Vosaroxin D1&D4	Decitabine
-3	50mg/mL	20 mg/m ² (Days 1-4)
-2	50 mg/m ²	20 mg/m ² (Days 1-5)
-1	70 mg/m ²	20 mg/m ² (Days 1-5)
0	90mg/m ²	20 mg/m ² (Days 1-5)

Phase II

Efficacy

The historical data suggested an ORR of 40% and with the assumption that the improved ORR is 60% the study will be stopped early if the observed patients' data suggest that:

$$\Pr(n > 0.6J \text{ data}) < 0.025$$

Here n is the overall response rate (ORR). That is, if at any time during the study we determine that there is a less than 2.5% chance that the average ORR is greater than 60%, we will terminate the study. The ORR is assumed to follow a non-informative prior of Beta (1.2, 0.8). The stopping boundaries for ORR, based on these assumptions and monitoring conditions are found in table 8. We will apply these stopping boundaries starting from the fifth patient and in cohorts of 5. For example, accrual will cease if only 2 or less than 2 patients experience overall response among the first 10 patients treated. The operating characteristics are summarized in table 8.

Table 8. Stopping boundaries for ORR

Number of patients evaluated	5	10	15	20	25	30	35	40	45	50	55	60
------------------------------	---	----	----	----	----	----	----	----	----	----	----	----

for response												
Number of patients with response (i.e., CR, CRp or CRi)	0	0-2	3-5	6-7	8-9	10-12	13-15	13-17	18-20	21-22	23-25	26-28

Table 9. Operating characteristics for monitoring of overall response rate

True overall Response Rate	Early Stopping Probability		Sample size		
			25%, 50%, 75%		
0.35	0.974		10	15	30
0.40	0.888		15	20	35
0.45	0.702		15	35	60
0.50	0.442		30	60	60
0.55	0.209		60	60	60
0.60	0.079		60	60	60
0.65	0.027		60	60	60

Toxicity Monitoring

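### Section 10.4 reports the primary ORR and its 95% interval with no allowance for the binding futility looks in section 10.3, so the estimate is biased low and a fixed-n exact interval under-covers near the 60% target

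*Combined protocol and SAP*

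**What the plan says.** Section 10.2 makes ORR (CR + CRp + CRi) the primary Phase II endpoint and sizes the trial as a single fixed sample: "With a null hypothesis of 40% historical response rate, a sample size of 60 patients would be required" to show 60%, "using a one-sample exact binomial test and with a two-sided alpha of 0.05 and a power of 82" percent. The 60 count the six Phase I patients treated at the MTD.

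Section 10.3 adds a Bayesian futility rule. The prior is Beta(1.2, 0.8), and if "there is a less than 2.5% chance that the average ORR is greater than 60%, we will terminate the study". On timing: "We will apply these stopping boundaries starting from the fifth patient and in cohorts of 5". The wording is mandatory; the worked example reads "accrual will cease if only 2 or less than 2 patients experience overall response among the first 10 patients treated". Table 8 lists the limits and Table 9 the resulting chance of stopping early, for example 0.888 at a true ORR of 40% and 0.079 at 60%.

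Section 10.4 then says "Response rates will be presented with 95% confidence intervals". It names no interval method, no estimator other than the response rate, and no adjustment for the looks. No other section supplies one.

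**The concern.** A trial that stops because its running response rate is low has a rate that is low partly by chance. Averaged over all the ways the trial can end, the plain proportion therefore underestimates the true rate. An interval that treats the attained number of patients as planned in advance inherits that shift.

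The rule fires when the data make 60% implausible. The early-stopped intervals that miss a true rate near 60% therefore miss on the low side.

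The ORR and its interval are the trial's main result and the figure that a later trial would use as a benchmark. At a true rate equal to the 40% historical value, the expected report would be about 33%, which would make the combination look worse than history when it is equal.

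**Working it through.** **Inputs.** Null 40%, target 60%, N = 60, exact test, two-sided 0.05 (section 10.2). Prior Beta(1.2, 0.8), criterion Pr(ORR > 0.60 | data) < 0.025, looks at 5, 10, ..., 60 (section 10.3). Limits are the upper end of each Table 8 cell: 0, 2, 5, 7, 9, 12, 15, 17, 20, 22, 25, 28.

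**The plan's own figures first.**
- Power: P(X ≥ 32 | 60, 0.40) = 0.02503, just above 0.025, so the critical value is 33. P(X ≥ 33 | 60, 0.60) = 82.2% (stated 82%), and P(X ≥ 33 | 60, 0.40) = 0.0133.
- Table 8: with x responses in n, the posterior is Beta(1.2 + x, 0.8 + n − x). The largest x with Pr(ORR > 0.60) < 0.025 reproduces all twelve limits. At n = 10, for instance, the probability is 0.008 for x = 2 and 0.038 for x = 3, so the limit is 2.
- Table 9: recomputed early-stopping probabilities are within 0.005 of those stated (see the table), with the same sample-size quartiles.

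**Enumeration.** Let P(n, x) be the probability of ending with x responses in n patients: the number of binomial paths that stay above every earlier limit, times p^x (1 − p)^(n − x). Early stops occur at n = 5 to 55; otherwise the trial ends at 60.
- Mean reported ORR = Σ P(n, x) · x/n.
- Clopper-Pearson limits: lower = 2.5% point of Beta(x, n − x + 1); upper = 97.5% point of Beta(x + 1, n − x).
- Coverage = Σ P(n, x) over outcomes whose interval contains p.

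| True ORR | Early stop, Table 9 | Early stop, recomputed | Mean x/n (%) | Bias (points) | Fixed-n exact coverage (%) |
|---|---|---|---|---|---|
| 35% | 0.974 | 0.975 | 28.10 | −6.90 | 98.53 |
| 40% | 0.888 | 0.889 | 33.04 | −6.96 | 98.77 |
| 45% | 0.702 | 0.697 | 38.65 | −6.35 | 97.61 |
| 50% | 0.442 | 0.438 | 45.05 | −4.95 | 97.82 |
| 55% | 0.209 | 0.213 | 51.80 | −3.20 | 95.05 |
| 60% | 0.079 | 0.082 | 58.30 | −1.70 | 92.71 |
| 65% | 0.027 | 0.026 | 64.23 | −0.77 | 94.05 |

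On a 1-point grid from 20% to 81%, the largest bias is −7.0 points, near 38%, and the lowest coverage is 91.6%, at 62%. Coverage falls below 95% only from 56% to 65%, apart from 94.9% at 53%.

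**Where the miss at 60% comes from.** With a fixed n of 60, the same interval covers 96.5%. Under the rule, 5.1% of intervals lie wholly below 60% and 2.2% wholly above (nominal 2.5% each). Early stops supply nearly all of the low misses: the trial stops with probability 0.082, and 61% of those intervals exclude 60%, so 0.082 × 0.61 ≈ 0.050.

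**Sensitivity to assumptions.**

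| Case | Bias at 40% (points) | Coverage at 60% (%) |
|---|---|---|
| As written, no overrun | −7.0 | 92.7 |
| First look at 10 | −5.4 | 93.3 |
| 5 extra patients analysed after a stop | −3.9 | 94.6 |
| 10 extra patients analysed after a stop | −2.6 | 95.3 |

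**The alternative.** Order outcomes by stopping look, then by responses. The lower limit solves P(this outcome or higher) = 0.025, and the upper limit solves P(this outcome or lower) = 0.025. This interval covers 95.4% at 60% and at least 95% at every rate checked. For 7/20 at a stop, the fixed-n exact interval is 15.4-59.2% and the stage-wise interval 17.8-63.8%. For 36/60 they are 46.5-72.4% and 46.6-72.7%.

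**The case against.** Much of the opposing case stands.

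- **The two effects do not peak together.** A reader might infer that the plan is 7 points off and under-covers at the same true rate. It is not so. At 35-40%, where the bias is about 7 points, the exact interval over-covers (98.5-98.8%). At 60%, where coverage is 92.7%, the bias is 1.7 points.
- **Overrun is likely.** Section 10.2 assesses response after one or two induction cycles, section 4.5 repeats treatment every 4-7 weeks, no accrual pause is written, and section 10.4 counts everyone given at least one dose. The no-overrun figures are therefore the upper end of the range above. The overrun counts of 5 and 10 are assumptions; the documents give none.
- **No false-positive problem.** A reader might suspect that repeated looks inflate type I error. These looks can only stop for futility. The chance of reaching 60 patients with at least 33 responses when the true rate is 40% is 0.012, against 0.0133 without looks.
- **The fixed-n method is inferred from silence.** Section 10.4 does not choose one. The exact interval is assumed here because section 10.2 uses an exact test. Wilson would cover 89.2% and Wald 87.3% at 60%, but the plan mentions neither.
- **The unbiased estimator is not simply better.** The root mean squared error of the uniformly minimum-variance unbiased estimate (UMVUE) is 0.095 against 0.108 for the raw proportion at 60%, but 0.148 against 0.150 at 40% and 0.155 against 0.150 at 35%. It also raises completed-trial results, for example 28/60 from 46.7% to 53.9%. This argues against replacing the raw proportion, not against reporting an adjusted figure beside it.

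None of this supplies the missing adjustment. The rule is binding as written, and Table 9 itself is matched by a calculation without overrun.

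**Conclusion.** The point holds as one about the accuracy of estimation. Section 10.4 makes no allowance for mandatory looks that, by the plan's own Table 9, end the trial early 88.8% of the time at a true ORR of 40% and 44.2% of the time at 50%.

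The consequence is a modest one-sided interval error in a band that contains the design target, and a larger downward bias at rates where the trial would probably stop. These sizes rest on three assumptions: the Table 8 limits are obeyed, no patients are analysed beyond a stopping look, and the interval is Clopper-Pearson. Stopping for toxicity was not modelled. The design's power, boundaries and false-positive risk are not in question, and a trial that ends with 36 responses in 60 would report almost the same interval either way.

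**What to change.** In section 10.4:
1. Name the interval method for the ORR.
2. Beside the raw proportion, report an exact 95% interval from stage-wise ordering of stopping look and number of responses under the Table 8 boundaries.
3. Add one bias-adjusted estimate, median-unbiased or UMVUE, chosen in advance.
4. State how patients treated beyond a stopping look enter the estimate and interval, since the stage-wise calculation shown here assumes none.

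The cost is a few lines of text and a short program, with no change to patients or data collection. Intervals are somewhat wider after an early stop. The UMVUE brings no uniform gain in mean squared error: the gain is negligible at about 40% and reverses at 35%. This is why it belongs beside the raw proportion and not in its place.

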of patient after discussion with the PI to optimize response if indicated. The re-induction must be given within 4-8 weeks of documented refractory leukemia. Re-induction (Induction 2) may be given beyond the stipulated 8 weeks if approved by the study PI.

If the bone marrow aspirate and/or biopsy(s) performed after the induction courses reveal a remission marrow (CR/CRp/CRi), then the patient may proceed to consolidation therapy at the discretion of the treating investigator. In addition, any clinically significant drug-related, nonhematologic toxicity experienced by a patient should return to < grade 2 or the baseline grade before the patient continues treatment.

Should the patient not achieve CR/CRp/CRi after the second induction course, they will be taken off study unless clinical benefit is observed and the PI approves continuation of therapy on the protocol.

Hydroxyurea 1.5 g orally daily for up to 10 days is allowed in the first induction course for white blood count $>30.0 \times 10^9/L$.

4.6 Post-remission Therapy in Phase I and Phase II:

Patients achieving a CR/CRp/CRi may receive consolidation/ maintenance therapy as follows:

Consolidation - Up to 5 additional cycles as follows:

- a. Vosaroxin intravenously on days 1 and 4 at a dose of 70 mg/m^2 for a total dose of $140 \text{ mg/m}^2/\text{cycle}$ (days 1 and 4). Decitabine at a dose of 20 mg/m^2 intravenously for 5 consecutive days (days 1-5), or the final induction dose determined in phase I.

Patients who achieve a CR/CRp/CRi should receive the consolidation cycle no sooner than 28 days from Day 1 of the previous induction or re-induction cycle provided their peripheral blood counts have recovered (ANC $\geq 1.0 \times 10^9/L$ and platelet count $\geq 50 \times 10^9/L$). If patient has documented CRp they may proceed with consolidation cycles even if the platelet count remains $\leq 50 \times 10^9/L$ if approved by the PI. If patient has documented CRi they may proceed with consolidation cycles even if the platelet count remains $\leq 50 \times 10^9/L$ and/or ANC $\leq 1.0 \times 10^9/L$ if approved by the PI.

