Bone marrow tests can be ordered more frequently if mandated by development of peripheral blood counts. No repeat bone marrow is necessary if nonresponse or progressive disease can be unequivocally diagnosed from peripheral blood tests or, in patients with a WBC < 0.3 if the bone marrow test is considered noncontributory by the investigator at any time point. Patient will be followed for survival at MD Anderson Cancer Center (MDACC) every 3 to 6 months for up to 5 years after completion of active treatment and while still on study. If the patient is unable to return to MDACC the follow-up visits may be conducted via telephone.

Concomitant medication data will not be collected or entered into the case report form; however, the subject's medication record will contain a list of concomitant medications.

Data regarding adverse events will be collected during the study. Please see **Appendix E** regarding data capturing of adverse events and adverse events source documentation. Protocol specific data will be entered into PDMS/CORe. PDMS/CORe will be used as the electronic case report form for this protocol. Only unexpected AEs will be recorded in the Case Report Form (CRF). The Principal Investigator will sign and date the AE log per each patient at the completion of each course. Following signature, the AE log will be used as source documentation for the adverse events for attribution.

Treatment may be discontinued for a variety of reasons, including patient withdrawal, investigator decision, and reasons specified by the protocol. Reasons for discontinuation of treatments are described below .

6.2 Follow-up Evaluations:

After completion of induction and consolidation treatment patients will continue to be followed at MDACC for 5 years.

Every 4-8 weeks, blood will be drawn for routine standard of care tests. If the patient cannot return to the MDACC clinic for blood draws, the blood draws can be set up at a local clinic closer to the patient's residence and the results reported to the research nurse for the study. The laboratory work done at the local clinic will be forwarded to the patient's attending physician at MDACC or PI of the study, who will sign off on the labs to verify that the results have been reviewed

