7.2.3 Criteria for Protocol-Defined Required Discontinuation of Treatment

The protocol requires discontinuation of study treatment for the following reasons:

1. Patient requests discontinuation.
2. There is unacceptable toxicity (i.e., NCI CTCAE version 4.0 clinically significant grade 4 drug-related non hematologic toxicity).
3. Patient experiences an NCI CTCAE version 4.0 \geq grade 3 drug-related non-hematologic toxicity or clinically significant infection of any grade that is not recovered by Day 75 from the onset of the toxicity.
4. Patient experiences a third occurrence of an NCI CTCAE version 4.0 clinically significant grade 3 drug related non-hematologic toxicity.
5. Patient experiences study drug related asymptomatic grade 2 total bilirubin or creatinine abnormality that is not recovered by Day 75 from the onset of the toxicity.
6. There is a need for any treatment not allowed by the protocol.
7. Treatment failure or disease relapses. Patients may continue if they are determined to have clinical benefit following discussion with the PI and the treating Physician. The discussion will be documented in the medical record.
8. Investigator discretion.

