7.2.4 Follow-Up at Treatment Discontinuation or Early Withdrawal

Patients who discontinue treatment for any reason will complete end-of-treatment procedures. End of treatment procedures will include a CBC with differential and platelets and a limited chemistry profile (total bilirubin, serum creatinine, SGPT or SGOT, potassium, magnesium, glucose). A bone marrow aspiration may be recommended only if non-response or progressive disease cannot be unequivocally diagnosed from peripheral blood. Although treatment will be discontinued at that time, all patients who do not withdraw consent for follow-up, die, or become lost to follow-up, will remain on study for follow-up evaluations. Subject will be followed for toxicity for at least 30 days after the last protocol treatment. The 30 day follow-up visit will be scheduled as a clinic visits for clinical evaluation and physical examinations. If the patient cannot make it to the MDACC clinic for this visit, the required follow up treatment procedure may be done with a local physician and the records forwarded to MDACC. The research nurse will contact the patient by telephone and get a verbal assessment of the patient's condition. The phone conversation will then be documented in the patients charts.

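### The protocol contradicts itself on whether patients taken off for non-response or toxicity stay in survival follow-up, and section 10.4 does not define drop-out or the overall survival censoring date

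*Combined protocol and SAP*

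**What the plan says.** **Leaving the study.** Section 4.5 (Phase II induction) reads: "Should the patient not achieve CR/CRp/CRi after the second induction course, they will be taken off study unless clinical benefit is observed", with approval of the principal investigator (PI) also needed for continuation. Section 4.3 has the same rule for Phase I. Section 4.7.3 uses the same off-study term for toxicity that recurs or persists at the lowest dose level, unless otherwise discussed with the PI.

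**Survival follow-up.** The sentence in section 6, Evaluations During Study, sets survival contact "every 3 to 6 months for up to 5 years after completion of active treatment and while still on study". Telephone contact is allowed.

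**After stopping treatment.** Section 7.2.3 opens "The protocol requires discontinuation of study treatment for the following reasons" and lists "Treatment failure or disease relapses" among them. Section 7.2.4 begins "Patients who discontinue treatment for any reason will complete end-of-treatment procedures" and states that "all patients who do not withdraw consent for follow-up, die, or become lost to follow-up, will remain on study for follow-up evaluations".

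**Analysis.** Section 8.6 defines OS from treatment start to death from any cause, with no censoring rule. Section 10.4 estimates OS by Kaplan-Meier in all patients with at least one dose and says "Patients who drop out of the study will be included in the time to event data as" censored. It defines neither drop-out nor the censoring date.

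**The concern.** Kaplan-Meier assumes that a patient censored at a given time has the same later risk of death as those still followed. A patient removed because two induction courses failed, or because toxicity persisted at the lowest dose level, is unlikely to meet that assumption. If survival contact ends at removal and the patient is then counted as a drop-out, later deaths are lost and the curve after that time describes mainly responders.

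OS is a stated Phase II secondary objective. The design's own response rates of 40% (null) and 60% (target) imply 60 × 0.60 = 36 or 60 × 0.40 = 24 non-responders among 60 patients. That is an upper limit on how many could be affected by the non-response wording. Early deaths, patients who never start a second course and PI-approved continuations all reduce it.

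**Working it through.** **1. The passages side by side**

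| Question | Sections 4.3, 4.5, 4.7.3 and the survival sentence in section 6 | Sections 7.2.3 and 7.2.4 |
|---|---|---|
| What ends at treatment failure? | Being on study | Study treatment |
| Who stays in follow-up? | Patients still on study | All except those who withdraw consent for follow-up, die or are lost |
| OS consequence under 10.4 | May be counted as a drop-out and censored | Not a drop-out; followed to death |

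Both columns apply to a patient without remission after the second induction course, and they give different answers. Section 10.4 does not say which applies.

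**2. Illustration of the size**

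The plan gives no OS median, event count or power, so there is no OS figure to reproduce.

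- From the documents: response rate p = 0.40 to 0.60 (section 10.2).
- Assumed: exponential survival with medians of 12 months in responders and 4 months in non-responders, so S_R(t) = 2^(−t/12) and S_N(t) = 2^(−t/4).
- Assumed: a fraction f of the non-responders alive at time c is censored at c.

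On timing, take a marrow at day 21, re-induction 4 to 8 weeks later, and a marrow 21 days after that. This gives 21 + 28 + 21 = 70 to 21 + 56 + 21 = 98 days, or 2.3 to 3.2 months at 30.4 days a month. One repeat marrow four weeks later moves the upper end to 126 days (4.1 months). So c = 2.5 is towards the early end and c = 4 towards the late end. Visit windows and further repeat marrows would widen this range.

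True survival: S(t) = p·S_R(t) + (1−p)·S_N(t).

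Large-sample Kaplan-Meier curve for t > c:

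S(c) × [p·S_R(t) + (1−f)(1−p)·S_N(t)] / [p·S_R(c) + (1−f)(1−p)·S_N(c)]

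*Worked case: p = 0.60, f = 1, c = 2.5.*
- S_R(2.5) = 0.8655 and S_N(2.5) = 0.6484.
- S(2.5) = 0.6 × 0.8655 + 0.4 × 0.6484 = 0.7787.
- Apparent median = 2.5 + 12 × log2(0.7787/0.5) = 2.5 + 7.67 = 10.2 months.
- True median: with x = 2^(−t/12), solve 0.6x + 0.4x³ = 0.5. Then x = 0.650 and t = 7.5 months.

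Median OS in months:

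| Response rate | True (and under 7.2.4) | All censored at 2.5 | Half censored at 2.5 | Half censored at 4 |
|---|---|---|---|---|
| 60% | 7.5 | 10.2 | 8.4 | 8.1 |
| 50% | 6.6 | 9.7 | 7.5 | 7.1 |
| 40% | 5.9 | 9.2 | 6.6 | 6.3 |

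With all censored at 3.5 months and a 60% response rate, 7.5 reads 9.5. If the two groups had equal hazards, the bias would be zero. It is upward whenever non-responders die faster than those still followed.

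**The case against.** The strongest reply is that section 7 already settles the matter. It treats treatment failure as a reason to stop treatment, covers stopping for any reason, and keeps such patients on study. On that reading the still-on-study limit excludes only those who withdraw consent, die or are lost. The separate Follow-up Evaluations text promises five years without that limit. The non-response trigger is also narrow: it needs failure of a second, optional course and has a PI-approved exception. Censoring genuine withdrawals and losses is ordinary practice.

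Much of this stands. A reader might infer that the plan instructs the analyst to censor non-responders. It does not: section 10.4 never calls them drop-outs, and 7.2.4 supports a reading with no bias. A reader might also infer that OS will be judged against the 7.7-month median reported for decitabine in the background section. The documents plan no such comparison; the historical rate in section 10 concerns response only.

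The reply does not remove the contradiction. Section 7.2.1 separates leaving treatment from leaving the study, so off study cannot safely be read as off treatment. Section 7.2.4 specifies end-of-treatment tests and at least 30 days of toxicity follow-up but does not mention survival. The five-year schedule starts after induction and consolidation are completed, which a non-responder does not reach. Staff could follow sections 4.5, 6 and 10.4 literally and believe they comply.

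**Conclusion.** The point holds as an internal contradiction combined with an undefined censoring rule, not as a stated rule that censors treatment failures. Its effect depends on which passage the site and the analyst follow. Under 7.2.4, bias from this source is zero. Under the off-study wording, median OS is overstated by 9.2 − 5.9 = 3.3 months (40% response rate) or 10.2 − 7.5 = 2.7 months (60%) if all surviving non-responders are censored at 2.5 months. If half are censored at 4 months, the overstatement is 0.4 to 0.6 months.

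The first of these is a worst case, and every figure rests on the assumed 12- and 4-month medians. The direction is firmer than the size. The change is worth making because OS is a stated objective and the remedy costs little. The primary response analysis and N = 60 are unaffected.

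**What to change.** 1. In sections 4.3, 4.5 and 4.7.3, reconcile the wording with 7.2.4 by writing off study treatment in place of off study wherever follow-up is meant to continue. Clarify in the same way the statements in 4.7.3 and 9.2 that a patient may be permanently withdrawn after an adverse event. This concerns follow-up only and leaves the criteria for stopping treatment as they are.
2. In the survival follow-up sentence of Evaluations During Study, delete the closing condition about still being on study.
3. In section 10.4, state that every treated patient is followed for survival. OS is censored only at the last date known alive, for withdrawal of consent for follow-up, loss to follow-up or data cut-off. Non-response, toxicity or stopping treatment is not a reason for censoring.

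The cost is wording, plus telephone contact that the protocol already allows. Reported OS may be shorter than under the off-study reading.
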